Table 3-2:	Definition of study periods	37
Table 3-3:	Definition of each 3-month period.....	40
Table 3-4:	Definition of each 6-month period.....	41
Table 3-5:	Study periods vs scheduled assessments.....	41
Table 3-6:	Dose group definitions for calculation of modal dose	46
Table 3-7:	Converting EpiTrack raw values to points.....	57
Table 3-8:	EpiTrack age corrections	58
Table 3-9:	Thresholds to define meaningful change	60
Table 10-1:	Exposure Duration Categories	75
Table 13-1:	Hematology, clinical chemistry, and endocrinology parameter abnormality criteria.....	87
Table 13-2:	Urinalysis parameters and possible values	89
Table 13-3:	Conversion of results in a five-point scale into a four-point scale	89
Table 13-4:	Urinalysis 4-point scales for PCS criteria	90
Table 13-5:	Vital signs and body weight PCS criteria	90
Table 13-6:	QTcB interval PCS criteria	92
Table 13-7:	Elevated liver function tests and Hy's Law criteria	92

VERSION HISTORY

This statistical analysis plan (SAP) for study EP0132 is based on the protocol amendment 2 dated 29MAR2021.

SAP Version	Approval Date	Change	Rationale
Original	15 Oct 2021	Not Applicable	Original version
Amendment 1	25 Oct 2024	
Sections 2.2.2, 3.13.2, and 3.13.4 Removed the term 'permitted' when referring to concomitant use of antiepileptic drugs (AEDs).
 
Section 3.12.1 Section added to explain the change from protocol with regards to removing the term 'permitted' when referring to the concomitant use of AEDs.
	A change from protocol. All AEDs may have an impact on the efficacy outcomes and should be considered in the analysis.
		
Section 2.2.2 Added timeframe to secondary efficacy endpoints.
 
Section 3.1 Added timeframe to secondary efficacy endpoints
 
Section 3.12.2 Section added to explain the change from protocol with regards to truncating the efficacy data up to Month 24 for the secondary efficacy endpoints.
	A change from protocol. Efficacy endpoints will be assessed up to Month 24.
		
Section 2.3.1
 
Update to clarify Down-Titration
	Down-Titration Period is not necessary if the participant has already reached a dose of

SAP Version	Approval Date	Change	Rationale
		Period attendance for participants who already reached a dose of 1mg/kg/day (50mg/day for study participants with body weight >50kg) at FV or EDV	1mg/kg/day (50mg/day for study participants with body weight >50kg) at FV or EDV
		Section 3.2 Clarification added regarding presentation of pharmacokinetic (PK) data.	To clarify that PK data is presented based on significant figures rather than decimal places.
		Section 3.3.1.3 Updated to consider an EDV as attended when the participant is not considered a completer as per Section 3.3.5	Consistency of completer definition
		Section 3.3.1.4 Section added to define the Final Visit (FV) and when this may occur.	
		Section 3.3.2 Definition of Overall Period added to the text and Table 3-2.	Overall Period is included in the planned tables but there was no definition in the SAP.
		Section 3.3.2 and 3.3.3 Text updated to use the date of the first dose in EP0132 as the start of the Evaluation Period and the start of the first 3 and 6 month periods instead of using the entry visit (EV) as the reference day.	The expectation was for the 1 st dose to be taken in the evening of the EV but this may not be the case for all participants and so the use of EV and day of 1 st dose, in derivations were inconsistent across the SAP.
		Section 3.3.2 Text added to clarify that the Evaluation Period may be truncated at Month 24 YEV for	To add clarity to Evaluation Period used for the absence seizure freedom analyses based on seizure diary data.

SAP Version	Approval Date	Change	Rationale
		the absence seizure freedom efficacy analyses based on seizure diary data.	
		Section 3.3.2 Text added to clarify that for participants who do not require down-titration at FV or EDV, the Overall Period includes the Evaluation Period and the Safety Period.	Down-Titration Period is not necessary if the participant has already reached a dose of 1mg/kg/day (50mg/day for study participants with body weight >50kg) at FV or EDV
		Section 3.3.2 Text added to clarify that for participants who complete the Study at FV, the Overall Period is the Evaluation Period	Down-Titration Period and Safety Period attendance is not necessary if the subject has completed the study at FV
		Section 3.3.2 Text added to Table 3-2 to clarify that for participants who do not require down-titration at FV, the Safety period starts the day after FV rather than the day after DTV	Down-Titration Period attendance is not necessary if the participant has already reached a dose of 1mg/kg/day (50mg/day for study participants with body weight >50kg) at FV
		Section 3.3.2 Text added to Table 3-2 to clarify that for participants who do not require down-titration at EDV, the Safety period starts the day after EDV rather than the day after DTV	Down-Titration Period attendance is not necessary if the participant has already reached a dose of 1mg/kg/day (50mg/day for study participants with body weight >50kg) at EDV
		Section 3.3.2 Text added to clarify attendance of the Down-Titration Period for participants	Consistency with Section 2.3.1

SAP Version	Approval Date	Change	Rationale
		who do not require down titration at FV or EDV	
		Section 3.3.3 Text added to include the type of summaries that will utilize 3 month periods versus 6 month periods. Table 3.5 and text added to clarify the difference in a study period and the timing of scheduled assessments. All tables extended past Month 24 for subjects who remain in EP0132 past 24 months. Clarified data inclusion for safety and efficacy summaries.	To acknowledge the difference in the definition of 3 and 6 monthly periods (eg, seizure diary data) and protocol defined scheduled assessments at 3 or 6 monthly intervals (electroencephalogram [EEG]). To fully describe mapping approach for visits past the expected end of study at Month 24. Efficacy is truncated at Month 24 but there is interest in safety data beyond Month 24.
		Section 3.3.4 Text added to include the date the World Health Organization (WHO) declared the end of the Coronavirus Disease 2019 (COVID-19) pandemic.	Added date when date became available (5 May 2023).
		Section 3.3.5 Text added to clarify completer definitions for participants who do not require down-titration	Down-Titration Period is not necessary if the participant has already reached a dose of 1mg/kg/day (50mg/day for study participants with body weight >50kg) at FV.

SAP Version	Approval Date	Change	Rationale
		Text added to clarify completer definitions for participants who are considered completers at FV by investigator	Complete possible scenarios for study completion.
		Section 3.3.6 For the data sources for the EP0132 EV, ethnic subgroup and physical examination have been removed from the list of variables to be obtained from the N01269 analysis database. Gender has been added to the list of data obtained from the N01269 analysis database. Added that height will be obtained from Visit 6 of N01269 if available and will otherwise be missing.	The EV of EP0132 will not obtain ethnic subgroup and physical examination from the N01269 database as these data were not collected. Height is not scheduled at Visit 7 or at an Early Discontinuation Visit (EDV) in N01269.
		Added that EV data for EpiTrack Junior and Pediatric Quality of Life Inventory (PedsQL) from the N01269 database brought across to the EP0132 EV will be listed only.	To add clarity to use of EP0132 EV assessments in summaries.
		Section 3.3.7 Detail added on how to handle assessments performed at an EDV.	To clarify how EDVs will be handled in the analysis.
		Section 3.3.8 Section added for the mapping of assessments performed at a FV.	To clarify how FVs will be handled in the analysis.

SAP Version	Approval Date	Change	Rationale
		
Section 3.3.9 Section added for the mapping of assessments performed at unscheduled visits.
 
Text added and amended for the handling of mapping unscheduled assessments for participants who stay in the study longer than 2 years.
	To clarify how unscheduled visits will be handled in the analysis.
		
Section 3.3.10 Text added to describe how a participant's dose can be maintained or modified. Removed reference to using the interactive voice or web response system (IXRS) vendor data for changes in the daily dose and instead use data captured in electronic case report form (eCRF).
 
Added the scenario in which the modal dose category will be calculated.
	IXRS vendor data is not available in the required format to define changes to dose.
		Section 3.11 Updated World Health Organization Drug Reference List version from SEP2017 to SEP2020.	The dictionary version for coding medications was updated during the study.
		Section 3.13.2 to 3.13.9 Replaced all references to rescue medication with any concomitant AED or benzodiazepines.	In EP0132 maintenance AEDs are allowed. From an efficacy perspective, all concomitant AED or benzodiazepines used

SAP Version	Approval Date	Change	Rationale
			as maintenance medication or as rescue medication have the potential to impact the efficacy of the study.
		Section 3.13.2 to 3.13.7 Text added and amended to clearly define how absence seizure freedom will be determined for each of the absence seizure freedom endpoints.	To add clarity to the derivation of the endpoints.
		Section 3.13.8 Text added to clarify how to use multiple assessments on the same day	To add clarity to the derivation of the endpoints.
		Section 3.13.8 and 3.1.9 Text added to clearly define consecutive absence seizures and cumulative consecutive absence seizures and provide additional information on how unscheduled assessments are handled.	To add clarity to the derivation of the endpoints.
		Section 3.13.10 Text added to clarify the source of the EpiTrack Junior scores at the EV in EP0132. Text added to clarify that the age correction is from the first time the EpiTrack Junior	Participants aged <6 will not have completed the

SAP Version	Approval Date	Change	Rationale
		score is completed and that the Baseline is available only for those who were aged 6 and above at N01269 Baseline.	EpiTrack Junior score at Baseline.
		Section 3.13.11 Text added to clarify that participants aged 2 to 4 will not have a baseline value for the PedsQL self-report and that the change from baseline (CFB) for the parent proxy report will not be calculated when the participant turns 5.	For participants aged 2 to 4 years old, there is no self-report version available and the parent proxy report includes fewer items than the versions for the older age groups and so is not comparable.
		Section 3.13.12 Removed reference to using the IXRS vendor data for changes in the daily dose and instead use data captured in eCRF. Formula for number of days the study participant received dose from which discontinued has been updated.	IXRS vendor data is not available in the required format to define changes to dose. Amended to reflect the scenario in which last dose is prior to date of discontinuation. '+1' added to correctly calculate the number of days on dose from which discontinued.
		Section 3.13.13 Dose at Adverse Event (AE) onset added.	New section added to provide detail on the derivation of dose at AE onset.
		Section 3.13.15 The derivation of the number of days on study drug has been updated to use the	The expectation was for the 1 st dose to be taken in the evening of the EV but this may not be the case for all participants.

SAP Version	Approval Date	Change	Rationale
		first dose in EP0132 instead of EV.	
		Section 4.1.3 Text added to clarify that the absence seizure is based on EEG.	Added text for completeness as sentence references EEG.
		Section 4.1.4.3 Text updated to split out the rules for handling medications with partial or missing dates when the medications are ongoing or not ongoing from N01269.	Added text for completeness.
		Section 4.1.4.4 Text updated to split out the rules for handling AEs with partial or missing dates when the AEs are ongoing or not ongoing from N01269. Added additional scenario of partial AE onset date and text for considering an AE to be treatment-emergent when the data are unclear or unavailable.	Added text for completeness.
		Section 4.1.4.5 Text updated to clarify the rules for handling study medication with partial stop dates.	Previously the text was written with the expectation that the date of last contact would be the date of death. However, the CRF Completion Guidelines state the date of last contact refers to the last contact whilst the participant was alive. If a participant dies, it is assumed that they

SAP Version	Approval Date	Change	Rationale
			continue on treatment until their death date and so no longer want to take the earliest date of last contact or death date.
		
Section 5.1.1 Removed summary of screen failures and specified details on screen failures are to be listed only.
 
For the overall summary and listing of disposition added new completer subcategory text for the number of participants who were prescribed BRV after EP0132 study.
 
Added text for the summary and listing of scheduled study visits. Also added a summary and listing of study periods.
 
For the listing, have added date of final contact
	
No screen failures data reported so far; thus it will suffice to list data that becomes available and a summary will no longer be required.
 
This is to provide clarity for how many participants completed the study were transitioned to another program and continued to be prescribed BRV after EP0132 study.
 
This was to clearly present the number of study visits attended by each participant and the number of 3-month study periods started and completed for each participant.
 
Align with the shell text.

		
Section 5.1.3 Removed reference to serious non-fatal AEs.
 
Clarified that only the most severe type of AE is taken.
	
Text was incorrect and has been updated to align with the standards.
 
Align with the shell text.

		Section 5.3 Removed description of COVID-19 data summaries.	No COVID-19 impact data reported so far thus it will suffice to list any data that becomes available and

SAP Version	Approval Date	Change	Rationale
			summaries will no longer be required.
		Section 6.1 Age at N01269 Visit 1 summaries removed. EudraCT and clinicaltrials.gov age categories added. Text added for countries to be summarized as part of the demographics summary.	Age at N01269 Visit 1 is not used anywhere in this study so summary of this data is not required. To align with N01269 and with reporting requirements. To align with disclosure and data transparency reporting requirements.
		Section 6.3 Summary of medical history removed.	Only the medical history not captured in N01269 are reported in EP0132 and so a listing of the data is deemed to be sufficient.
		Section 6.4 Detail regarding AED groupings for previous and concomitant medications has been updated.	The physician reviewed spreadsheet of AEDs has been updated, so this section now refers to the spreadsheet rather than listing the medications in each group.
		Section 8.1 Detail added for determination of the denominators to be used in the calculation of percentages for the summaries. Text added to explain that the secondary efficacy variables will not be summarized for visits or periods beyond scheduled Month 24 YEV for	To add clarity on how the percentages will be calculated. To add clarity that the secondary efficacy variables will not summarize the visits/periods beyond Month 24 that are only available for small

SAP Version	Approval Date	Change	Rationale
		
participants who continue in the study beyond 2 years.
 
Section 8.1.1 to 8.1.7 Text amended to clearly distinguish between scheduled MEV/FEV/YEV visits and monthly periods.
	
subset of participants that continued in the study beyond 2 years.
 
To add clarity to the secondary efficacy endpoints being summarized.

		
Section 8.1.1 and 8.1.3 Added text for a new sub-category to be summarized under the number participants that are not absence seizure free. These are participants who discontinued the study prior to Month 24 and are imputed as not absence seizure free.
	
To clarify how many discontinued participants have been imputed as not absence seizure free per each scheduled assessment or monthly period.

		
Section 9.1 Removed reference to post-dose PK samples.
 
Text added describing the details to be provided in the PK listing, including the addition of previous dose date and time and time since previous dose.
 
Removed reference to using the IXRS vendor data for changes in the daily dose and instead use data captured in eCRF.
	
Per the protocol, only pre-dose PK samples are planned.
 
To clarify that the pre-dose PK samples are to be compared to the timing of the previous dose and not the post-dose.
 
IXRS vendor data is not available in the required format to define changes to dose.

SAP Version	Approval Date	Change	Rationale
		
Section 10.1 Text added to specify the inclusion of participant years of exposure in the summary table and provide its definition.
 
In Table 10-1 and the following text, the wording was changed from Exposure Duration Cohorts to Exposure Duration Categories.
 
For the modal dose exposure summary, the wording for overall summary changed to all participants.
 
Removed reference to using the IXRS vendor data for changes in the daily dose and instead use data captured in eCRF.
 
Text added to define the prescribed starting dose and the dose at subsequent visits.
	
Participant years of exposure was being included in the corresponding summary table but was not defined in the SAP.
 
To clarify the exposure durations are categories and not cohorts.
 
To help distinguish between all participants in the Evaluation Period and the Overall Period .
 
IXRS vendor data is not available in the required format to define changes to dose.
 
Starting dose is not captured in the eCRF so needs to be assumed based on the protocol information.

		Section 10.2 Removed reference to using the IXRS vendor data for changes in the daily dose and instead use data captured in eCRF.	IXRS vendor data is not available in the required format.
		Section 10.2 and 10.2.1 Text added to	To add clarification on the AE plain language

SAP Version	Approval Date	Change	Rationale
		describe the AE summaries to be reported for the plain language summary.	summary reporting. This is to be reported outside of the CSR.
		Section 10.2 and 10.2.1 Text added to clarify the periods to be summarized for each AE summary.	To add clarification which AE summaries are to be produced on the Overall Period, Evaluation Period and for each 3-month period in the Evaluation period.
		Section 10.3.1 Text added to clarify the inclusion of laboratory variables from central/local laboratories for study participants with possible clinically significant treatment-emergent (PCST) values.	To add clarification regarding the presentation of PCST values.
		Section 10.5.1 Removed text regarding truncating the non-absence seizure 1-hour EEG data at Month 24.	Non-absence seizures are part of primary safety objective hence all data will be reported in the summary of non-absence seizures.
		Section 10.5.1 and 10.5.2 Text added to clarify the inclusion of assessments post Month 24 in summaries.	To add clarification for the summaries.
		Section 10.6.1 Text added to clarify that participants who turn the age of 18 before or on the first scheduled EpiTrack Junior assessment will be excluded from all summaries.	Protocol states that EpiTrack Junior in EP0132 is only required for participants <18 years of age, and original text was not clear on how to handle the participants who are 18 or turn 18 during EP0132.

SAP Version	Approval Date	Change	Rationale
		Section 10.6.2 Text added to clearly describe what data will be included for participants aged 2 to 4 years old and that participants will be included in the summaries by age group based on their age at N01269 baseline.	Original text was not clear on the handling of PedsQL scores for participant's aged 2 to 4 years old plus which summary the participant is reported in as their age enter the older age groups.
		Sections 13.1.1 (Table 13-1), 13.1.3 (Table 13-5), and 13.1.4 (Table 13-6) updated to remove any age categories not applicable to EP0132. Section 13.1.1 (Table 13-1) also updated to present the abnormality criteria in International System of Units (SI). Table 13-6 age category updated to remove > from “>12y- <17y”.	To align text with the age categories relevant to EP0132. Ensure text aligns with the reporting of laboratory values in SI units. Updated following actions resulting from N01269 DEM-A review.
		Section 13.1.3 Clarification added and amended regarding the methodology to be used to determine Body Weight possibly clinically significant (PCS) criteria.	To add clarification regarding the body weight PCS criteria.

LIST OF ABBREVIATIONS

List of Abbreviations

AE	adverse event
AED	antiepileptic drug
ATC	anatomical therapeutic chemical
BLQ	below the limit of quantification
BMI	body mass index
BRV	brivaracetam
CAE	childhood absence epilepsy
CFB	change from baseline
CI	confidence interval
COVID-19	Coronavirus Disease 2019
CSR	clinical study report
C-SSRS	Columbia Suicide Severity Rating Scale
DBP	diastolic blood pressure
DEM	data evaluation meeting
DTV	Down-Titration Visit
ECG	electrocardiogram
eCRF	electronic case report form
EDV	Early Discontinuation Visit
EEG	electroencephalogram
EV	Entry Visit
FAS	Full Analysis Set
FEV	Full Evaluation Visit
FV	Final Visit
GTCS	generalized tonic-clonic seizure
HRQoL	health-related quality of life
HV	hyperventilation
ICH	International Council for Harmonisation of Technical Requirements for Pharmaceuticals for Human Use
ILAE	International League Against Epilepsy
IPD	important protocol deviation

List of Abbreviations

IXRS	interactive voice or web response system
JAE	juvenile absence epilepsy
LLOQ	lower limit of quantification
LTFU	long-term follow up
MCID	minimal clinically important difference
MedDRA	Medical Dictionary for Regulatory Activities
MEV	Minimal Evaluation Visit
nR	new ratio
PCS	possibly clinically significant
PCST	possibly clinically significant treatment-emergent
PDILI	potential drug-induced liver injury
PedsQL	Pediatric Quality of Life Inventory
PK	pharmacokinetic
PKAS	Pharmacokinetic Analysis Set
PLS	Plain Language Summaries
POS	partial onset seizure
PT	Preferred Term
SAE	serious adverse event
SAP	statistical analysis plan
SDTM	Study Data Tabulation Model
SBP	systolic blood pressure
SD	standard deviation
SFU	Safety Follow-up
SI	International System of Units
SOC	System Organ Class
SS	Safety Set
SV	Safety Visit
TEAE	treatment-emergent adverse event
UV	Unscheduled Visit
WHO	World Health Organization
YEV	Yearly Evaluation Visit

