4.1.4.5 Handling of study medication with partial or missing date

No imputation should be performed for missing study medication start dates. This field on the eCRF should not be partial or missing.

The last dose of study medication for participants who down-titrate will be the last dose during the Down-Titration Period; for participants who do not down-titrate, the last dose of study medication will be the date of either the EDV or the FV (unless the participant reports stopping study medication earlier). For partial or missing date of last dose of study medication on the Study Termination eCRF, the following imputation rules will be applied for the purpose of calculating overall exposure:

- If only the month and year are specified, impute the last dose date as the earliest of the last day of the month or the date of last contact reported on the Study Termination eCRF. If the participant has died during the month use the date of death if this is earlier
- If only the year is specified, impute the last dose date as the earliest of the last day of the year or the date of last contact on the Study Termination eCRF. If the participant has died during the year use the date of death if this is earlier
- If the last dose date is completely unknown on the Study Termination eCRF and no information could be obtained from data cleaning exercises, then use the date of last contact unless the participant has died during the year, in which case use the date of death. A review of the data for study participants with completely unknown last dose dates should be performed to ensure that the imputation does not result in an unrealistic value for duration of exposure

Imputed date of last dose dates should only be used for calculation of the duration of exposure. The date as recorded on the eCRF should be presented in study participant data listings (no imputed dates should be included in study participant data listings).

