10.2 Adverse events

Adverse events will be summarized as reported on the EP0132 eCRF without integration of events from the N01269 analysis database. Any AEs that are ongoing at the time of entry into EP0132 will be entered on the EP0132 AE eCRF.

All AEs in this study will be classified as pre-treatment or treatment-emergent. In the following definitions, first dose of BRV refers to the first dose in EP0132. Pre-treatment AEs are defined as AEs which had an onset date prior to the first dose of BRV. Treatment-emergent adverse events are defined as AEs that had onset on or after the day of first dose of BRV. All summaries of TEAEs will be based on the SS. Summaries of TEAEs will be produced for the Overall Period, the Evaluation Period, and for each 3-month period in the Evaluation Period (as defined in [Table 3-3](#)), more details on the requirements of each period for each summary are provided in [Section 10.2.1](#).

For the reporting of UCB plain language summaries (PLS) additional summaries of TEAEs will be reported based on the SS. These will only be produced for the Overall Period.

For all summaries (with the exception of TEAEs leading to permanent discontinuation of study drug) the intercurrent event of treatment discontinuation is handled by using a while-on-treatment strategy where observation ends 14 days after treatment is stopped. Thus summaries will include all TEAEs with onset on or after the day of the first dose of BRV up to and including the date of last dose of BRV + 14 days, where missing or partial date of last dose is handled as described in [Section 4.1.4.5](#).

The standard AE eCRF has the outcome of “worsened” to be used when there is an increase in the intensity of an AE. The definition of “worsened” is when the AE is still present but at a heightened intensity. The eCRF instructions dictate to complete a new AE screen with the event term of the worsened event.

Note that the outcome of “worsened” is not allowed terminology within the CDISC standards. In the SDTM.AE, the data is mapped to the outcome “Not Recovered/Not Resolved”. The outcome of “Worsened” will be kept in SDTM.SUPPAE.

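### SAP 4.1.4.5: when a participant dies with a partial last-dose date, the date-of-death clause read literally never takes effect, so the imputed last dose can stop at last contact

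*SAP*

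**What the plan says.** SAP 4.1.4.5 gives three rules for an incomplete last-dose date on the Study Termination eCRF:

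- Month and year known: "impute the last dose date as the earliest of the last day of the month or the date of last contact". A second sentence adds: "If the participant has died during the month use the date of death if this is earlier".
- Year only: "the earliest of the last day of the year or the date of last contact", followed by "If the participant has died during the year use the date of death if this is earlier".
- Nothing known and not recoverable by data cleaning: "then use the date of last contact unless the participant has died during the year, in which case use the date of death".

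The section closes by restricting imputed last-dose dates to the calculation of exposure duration. SAP 10.2, however, limits every TEAE summary except TEAEs leading to permanent discontinuation to onset "up to and including the date of last dose of BRV + 14 days, where missing or partial date of last dose is handled" under that same section.

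The Version History entry for 4.1.4.5 explains what last contact means in the CRF: "the CRF Completion Guidelines state the date of last contact refers to the last contact whilst the participant was alive". It gives the reasoning behind the amended rule as the assumption that participants who die "continue on treatment until their death date and so no longer want to take the earliest date of last contact or death date".

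SAP 4.1.4.3, on concomitant medications, sets a partial stop date to period end, or to the date of death if the participant died within that period. It does not use last contact.

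**The concern.** The third rule follows the stated assumption of treatment until death, but the first two do not appear to. Their death clause can act only if death precedes last contact, which the CRF definition excludes. One deceased participant with identical partial stop dates could therefore get one end date for brivaracetam and a later one for a concomitant drug.

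The first consequence is exposure duration (SAP 10.1), which feeds participant-years and the duration categories. The second is conditional. If the imputed date also closes the 14-day window, a fatal AE starting after it drops out of the TEAE, serious TEAE and fatal TEAE summaries. Safety is the primary objective, and Protocol Table 8-2 lists sudden unexpected death in epilepsy as an anticipated SAE.

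**Working it through.** The plan states no figure to reproduce; this is a check of a date rule.

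**Inputs.** E is the last day of the recorded month or year. C is the date of last contact. D is the date of death. The Version History definition gives C ≤ D.

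**Literal rule, first two bullets.** Start with R = min(E, C). If death fell in the recorded period and D < R, use D instead. Since min(E, C) ≤ C ≤ D, the condition D < R is never met, and the result is always min(E, C).

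**Enumeration.** I applied the rule to every date pair with C ≤ D in a 365-day year:

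- *Month and year known, both dates in the recorded month.* There are 7×496 + 4×465 + 406 = 5,738 pairs. All return last contact; 365 are same-day ties. The largest gap from imputed last dose to death is 30 days, and 1,523 pairs have a gap above 14 days.
- *Year only, both dates in the recorded year.* There are 365×366/2 = 66,795 pairs. All return last contact, with 365 ties. The largest gap is 364 days.

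These counts cover possible dates. They are not probabilities.

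**Hypothetical cases, dates in 2023:**

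| Case | Recorded last dose | Last contact | Death | Current rule | Gap to death | Current rule + 14 days | Under the fix |
|---|---|---|---|---|---|---|---|
| A | March | 3 Mar | 28 Mar | 3 Mar | 25 days | 17 Mar | 28 Mar |
| B | Year only | 3 Mar | 20 Jun | 3 Mar | 109 days | 17 Mar | 20 Jun |
| C | June | 5 Apr | 20 Jun | 5 Apr | 76 days | 19 Apr | 20 Jun |
| D | March | 10 Apr | 20 Apr | 31 Mar | 20 days | 14 Apr | 31 Mar |
| E | Unknown | 3 Mar | 20 Jun | 20 Jun | 0 days | 4 Jul | 20 Jun |

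B and E share the same contact and death dates. Knowing the year shortens exposure by 109 days compared with knowing nothing. In C the imputed date falls before the month that was recorded. D shows the limit of the problem: when last contact is after period end, the rule returns period end and the fix changes nothing.

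**Effect on AE summaries.** In case A, a fatal AE with onset on 28 March lies after 17 March, so it is left out if SAP 10.2 governs. With the last dose set to death, the window would run to 11 April and include it.

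**The case against.** **A reading that rescues the clause.** The death sentence stands apart and could be compared with period end alone. It would then match the third rule and the stated aim. But a death within the recorded month or year is never later than period end, so the words making it conditional on being earlier would be almost redundant. The ambiguity is genuine, and the text needs correcting on either reading.

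**The exposure-only sentence.** A reader might infer that fatal events are certainly lost from the TEAE summaries. The documents do not settle this, because the restriction in 4.1.4.5 and the cross-reference in 10.2 contradict each other. The default in SAP 4.1.4.4, which treats an undeterminable AE as treatment-emergent, leans towards inclusion. However, that section separates pre-treatment from treatment-emergent events and does not address the 14-day cut.

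**What stays visible.** A reader might also infer that such an event ceases to be a TEAE. It does not: the definition in 10.2 has no upper time limit, and the 14 days restrict only the summaries. The cut works on onset, so an AE that starts inside the window and proves fatal later is counted. Excluded events stay in the listings and can appear in the overall-summary row for AEs leading to death, which uses the screened set.

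**A percentage.** Visit spacing of about 91 days suggests (91−14)/91 = 85% of deaths falling beyond the window. That assumes contact only at scheduled visits, deaths spread evenly, and onset on the day of death. With contact every 30 days the same formula gives 53%, and every 14 days 0%. The documents give no contact interval for participants who die, so none of these figures is usable.

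**The amendment log.** A difference between the log and current text is not itself an error. The defect rests on current 4.1.4.5, its third rule and 10.2; the log supplies only the meaning of last contact and the intent.

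**Conclusion.** Wrong as written, low impact. Read literally, the death clause in the first two rules has no effect. Where last contact is on or before period end, the imputed last dose is last contact, which conflicts with the third rule, with 4.1.4.3 and with the assumption of treatment until death. Per participant, the shortfall against death reaches the 30-day and 364-day limits shown above, and can be larger when last contact precedes the recorded period.

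This rests on the CRF meaning of last contact and the literal reading. The loss of a fatal AE from the TEAE summaries needs two further conditions: 10.2 prevails over the exposure-only sentence, and onset is more than 14 days after the imputed date. It is a possible consequence, not an established one. About 140 participants may enroll, and only those who die with a partial last-dose date are concerned, so numbers should be small.

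**What to change.** In the first two rules of SAP 4.1.4.5, write: *If the participant died, impute the earlier of the last day of the recorded month (or year) and the date of death; date of last contact is not used.* Keep the last-contact rule for participants not known to have died.

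In the third rule, make the condition death during the study instead of death during the year, since no year is known there.

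Reconcile the exposure-only sentence with 10.2 by stating that the imputed date also sets the last dose + 14 days window.

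The cost is a few sentences in the SAP and the matching derivation code. No new data are needed.
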